5.5 Withdrawal of Subjects and Discontinuation of Study

AbbVie may terminate this study prematurely at any time, either in its entirety or partially (discontinue one or more treatment groups), or at any site. The study may be discontinued or terminated in case of an unacceptable risk, any relevant toxicity, or a negative change in the risk/benefit assessment. This might include the occurrence of AEs with a character, severity or frequency that is new in comparison to the existing risk profile. In addition, data derived from other clinical trials or toxicological studies which negatively influence the benefit-risk assessment might cause discontinuation or termination of the study. The investigator may also stop the study at his/her site if he/she has safety concerns. If AbbVie terminates the study for safety reasons, AbbVie will promptly notify the investigator. Advance notice is not required by either party if the study is stopped due to safety concerns.

A subject may voluntarily withdraw from the study at any time for any reason. An investigator may discontinue a subject's participation at any time for any reason. The AbbVie Therapeutic Medical Director may mandate individual subject discontinuation from study drug in case of a safety concern.

Subjects must have study drug discontinued immediately if any of the following occur:

- Abnormal laboratory result or AE that meets the criteria for discontinuation of study drug as stated in Section 6.2, or rule out safe continuation of the study drug as determined by the investigator or the AbbVie Therapeutic Area Medical Director.
- Serious infections (e.g., sepsis) that cannot be adequately controlled within 2 weeks by anti-infective treatment or would put the subject at risk with continuation of the study drug.
- Subject is non-compliant with TB prophylaxis (if applicable) or develops active TB at any time during the study.
- Malignancy, except for localized NMSC or carcinoma in-situ of the cervix.
- The subject develops anaphylactic reactions or anaphylactic shock.
- The investigator believes it is in the best interest of the subject.

- The subject requests withdrawal from study drug or the study.
- Eligibility criteria violation was noted after the subject started study drug and continuation of the study drug would place the subject at risk.
- Introduction of prohibited medications or dosages and continuation of the study drug would place the subject at risk.
- The subject becomes pregnant while on study drug.
- Subject is significantly noncompliant with study procedures, which would put the subject at risk for continued participation in the trial as determined by the Investigator or AbbVie Therapeutic Medical Director.

State of Emergency or Pandemic-Related Acceptable Protocol Modification

During the COVID-19 pandemic, it has been necessary to employ mitigation strategies to enable the investigator to ensure subject safety and continuity of care. Acceptable mitigation strategies are identified and included in the Operations Manual in [Appendix G](#).

The investigator should contact the sponsor medical contact before discontinuing a subject from the study for a reason other than described in the protocol to ensure all acceptable mitigation steps have been explored.

Treatment Group Changes

Treatment group changes at Week 12 (e.g., the re-randomization of subject on placebo) will be done by interactive response technology (IRT) to ensure double-blind integrity.

5.6 Follow-Up After Subject Discontinuation of Study Drug or from Study

Discontinuation of Study Drug and Continuation of Study Participation

To minimize missing data for efficacy and safety assessments, subjects who prematurely discontinue study drug treatment should be encouraged to continue to be followed for all regularly scheduled visits as outlined in the [Appendix E](#), and adhere to all study procedures except for administration of study drug, annual TB testing, and PK sample collection, unless a subject decides to discontinue study participation entirely (withdrawal of informed consent). Subjects should continue to be advised on the scientific importance of their data even if they discontinue treatment with study drug early. Following the discontinuation of study drug, the subject should be treated in accordance with the investigator's best clinical judgment irrespective of whether the subject decides to continue participation in the study.

In addition, a 30-Day Follow-up Phone Call and a 70-Day Follow-up Visit after the last dose of study drug is required to ensure all treatment-emergent AEs/SAE have been resolved. All attempts must be made to determine the date of the last study drug dose and the primary reason for discontinuation of study drug or study participation. This information will be recorded on the appropriate eCRF page. This Follow-up Phone Call is not applicable for subjects who discontinue study drug prematurely and continue study participation with completion of at least 1 study visit at least 30 days after the last dose

of study drug. This Follow-up Visit is not applicable for subjects who discontinue study drug prematurely and continue study participation with completion of at least 1 study visit at least 70 days after the last dose of study drug.

Premature Discontinuation of Study (Withdrawal of Informed Consent)

If a subject prematurely discontinues study participation (withdrawal of informed consent), the procedures outlined for the Premature Discontinuation visit should be completed as soon as possible, preferably within 2 weeks, and preferably prior to initiation of another therapy.

For subjects to be considered lost to follow-up, reasonable attempts must be made to obtain information on the subject's final status. At a minimum, 2 telephone calls must be made, and 1 certified letter must be sent and documented in the subject's source documentation.

If a subject withdraws from study follow up or withdraws permission for the collection of their personal data, the study staff may still use available public records to obtain information about survival status only, as appropriate per local regulations.

5.7 Study Drug

ABBV-154 or placebo only will be manufactured and provided by AbbVie. It will be taken as SC injections in the abdomen or thigh beginning on Day 1 (Baseline). The study drug (ABBV-154 or placebo) will always be administered by a healthcare/ trained professional up to Week 78 (end of LTE Period 1). For LTE Period 2, study drug will be administered to all subjects by either site medical staff on-site or by the subject or designee (friend, family member, or personal health care professional), if opted for home dosing and where locally permitted. It should be taken at approximately the same time eow, preferably between 7 am and 11 am. A 15- to 30-minute post administration observation time is required. The study drug can be taken with or without food.

ABBV-154 and placebo syringes will be packaged in cartons with quantities sufficient to accommodate the study design. Each prefilled syringe and carton will be labeled per local requirements and these labels must remain affixed to the syringe and carton. Upon receipt, study drug should be stored as specified on the label (refrigerated at 2 to 8 degrees Celsius) and kept in a secure location. Each kit will contain a unique kit number. This kit number is assigned to a subject via Interactive response technology IRT and encodes the appropriate study drug to be dispensed at the subject's corresponding study visit. Study drug must not be dispensed without contacting the IRT system. Site staff will complete all blank spaces on the label before dispensing to subjects. Study drug is for investigational use only and will only be used for the conduct of this study.

AbbVie will provide instructions for drug preparation.

Table 2. Identity of Investigational Product

Study Drug	Dosage Form	Strength	Route of Administration	Manufacturer
ABBV-154	Solution for injection/infusion in pre-filled syringe	40 mg and 150 mg	subcutaneous	AbbVie
Placebo for ABBV-154	Solution for injection/infusion in pre-filled syringe	Not applicable	subcutaneous	AbbVie

5.8 Randomization/Drug Assignment

All subjects will be assigned a unique identification number by the IRT at the screening visit. For subjects who rescreen, the screening number assigned by the IRT at the initial screening visit should be used. The IRT will assign a randomization number that will encode the subject's treatment group assignment according to the randomization schedule.

At Baseline, 425 subjects will be randomized to 5 treatment groups in a 1:1:1:1:1 ratio to receive ABBV-154: 40 mg, 150 mg, 340 mg SC eow; 340 mg SC e4w, or placebo. Randomization will be stratified by Baseline glucocorticoid (yes/no); number of prior failed b/tsDMARDs (1; 2 or more); and prior anti-TNF failure (yes/no) and if yes further stratification by prior adalimumab use (yes/no). At Week 12, subjects assigned to placebo will be re-randomized in a 1:1 ratio to receive ABBV-154 150 mg or 340 mg SC eow; subjects from the other dose groups will continue with their respective dose and dosing regimen. Re-randomization will be stratified by baseline glucocorticoid use (yes/no) and prior adalimumab use (yes/no). The enrollment for subjects with prior adalimumab use is capped at approximately 30% of the total subjects enrolled.

All AbbVie personnel with direct oversight of the conduct and management of the trial (except for AbbVie Drug Supply Management Team) will be blinded to each subject's treatment through Week 12. The study site personnel and the subject will remain blinded throughout the study. To maintain the blind, the ABBV-154 and placebo pre-filled syringes provided for the study will be identical in appearance. The IRT will provide access to unblinded subject treatment information in the case of a medical emergency.

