4 INVESTIGATIONAL PLAN

4.1 Overall Study Design and Plan

This is a randomized, double-blind, Phase 2b, dose-ranging study with a 12-week Placebo-Controlled Period, a 66-week Double-Blind Long-Term Extension (LTE) Period 1, a 104-week LTE Period 2, and a 70-Day Follow-up Period in adults with moderately to severely active RA and on background MTX, who have had an inadequate response to b/tsDMARDs treatment.

Subjects will remain on a stable dose of MTX until Week 24 (unless qualifying rescue therapy as described in [Section 5.4](#)); thereafter MTX may be adjusted within the range of 7.5 – 25 mg/week. At Baseline, 425 subjects will be randomized to 5 treatment groups in a 1:1:1:1:1 ratio to receive ABBV-154 at either 40 mg, 150 mg, 340 mg, subcutaneously (SC) every other week (eow); 340 mg SC every 4 weeks (e4w); or placebo SC eow. Randomization will be stratified by Baseline glucocorticoid (yes/no); number of prior failed b/tsDMARDs (1; 2 or more); and prior anti-TNF failure (yes/no) and if yes further stratification by prior adalimumab use (yes/no). At the end of the Week 12 Visit, subjects previously on placebo will be re-randomized and will receive ABBV-154 150 mg SC eow or ABBV-154 340 mg SC eow. At re-randomization, subjects will be stratified by baseline glucocorticoid use (yes/no) and prior adalimumab use (yes/no). Subjects from the other dose groups will continue with their respective dose and dosing regimen. The enrollment for subjects with prior adalimumab use is capped at approximately 30% of the total enrolled subjects.

Systemic glucocorticoids (dose of ≤ 7.5 mg/d prednisone equivalent at Baseline) must be tapered off within 4 weeks of the start of study drug.

[figure not shown]
The Primary Analysis will be conducted after all ongoing subjects have completed Week 12 or have withdrawn from the study. After the Primary Analysis, additional analyses may be conducted as needed. A final analysis will be conducted after all subjects have completed LTE Period 2 and a safety follow-up visit or have withdrawn from the study. To maintain integrity of the trial, the study sites and subjects will remain blinded until all subjects have either completed the last visit of LTE Period 1 or have withdrawn from the study. The AbbVie study team will be unblinded to treatment assignment after the Primary Analysis.

The schematic of the study is shown in [Figure 1](#).

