APPENDIX F. PROTOCOL SUMMARY OF CHANGES

Previous Protocol Versions

Protocol	Date
Version 1.0	23 April 2021
Version 1.1 (Japan Only)	10 May 2021
Administrative Change 1	06 July 2021
Version 1.2 (United Kingdom Only)	17 September 2021

The purpose of this version is to update the following sections below. In addition, minor typographical corrections or edits have been made for consistency throughout the Protocol and Operations Manual.

Summary of Protocol Changes:

- Protocol Section 1, Synopsis; Protocol Section 4.1, Overall Study Design and Plan: Added a 104-week LTE Period 2 and renamed the originally planned double-blind LTE period "Double-Blind, Long-term Extension Period 1." Corrected spelling of glucocorticoid.

Rationale: *The 2 LTEs are labeled "Double-Blind, Long-term Extension Period 1" and "Long-term Extension Period 2" to differentiate between them as the first LTE period is double-blind and the second LTE period will be blinded only until the last subject completes the last visit of Double-Blind Long-term Extension Period 1 or withdraws from the study. The 104-week LTE Period 2 will collect additional data for the long-term safety, tolerability, and efficacy of ABBV-154 in subjects with RA who have completed Double-Blind LTE Period 1.*

- Protocol Section 1, Synopsis, Investigational Plan: Follow-up "Visit" changed to Follow-up "Period."

Rationale: *To reflect the duration of follow-up, as the follow-up period is now comprised of a follow-up phone call and a follow-up visit as opposed to a single visit.*

- Protocol Section 1, Synopsis; Protocol Section 4.1, Overall Study Design and Plan; Protocol Section 7.1, Statistical and Analytical Plans: Updated wording to indicate that blinded dosing regimens will be continued until all subjects having either completed the last visit of LTE Period 1 or have withdrawn from the study.

Rationale: *To specify when unblinding will occur.*

- Protocol Section 1, Synopsis; Protocol Section 5.1, Eligibility Criteria: Updated criterion #7 to include a list of b/tsDMARDs that can be considered for the criteria of inadequate response, including guidance for previous use of investigational drugs. Updated note on the criterion #7 to clarify that b/tsDMARDs discontinued due to other reasons unrelated to inadequate response will not be accepted to fulfill eligibility criteria.

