2.3 Treatment Assignment and Blinding

Subjects will remain on a stable dose of MTX until Week 24 (unless qualifying for rescue therapy as described in Protocol Section 5.4); thereafter MTX may be adjusted within the range of 7.5 – 25 mg/week. At Baseline, approximately 425 subjects will be randomized to 5 treatment groups in a 1:1:1:1:1 ratio to receive ABBV-154: 40 mg, 150 mg, 340 mg SC EOW; 340 mg SC E4W, or placebo. Randomization will be stratified by Baseline glucocorticoid (yes/no); number of prior failed b/tsDMARDs (1; 2 or more); and prior anti-TNF failure (yes/no) and if yes further stratification by prior adalimumab use (yes/no). At Week 12, subjects assigned to placebo will be re-randomized in a 1:1 ratio to receive ABBV-154 150 mg or 340 mg SC EOW; subjects from the other dose groups will continue with their respective dose and dosing regimen. Re-randomization will be stratified by Baseline glucocorticoid use (yes/no) and prior adalimumab use (yes/no). The

enrollment for subjects with prior adalimumab use is capped at approximately 30% of the total subjects enrolled. Systemic glucocorticoids (dose of ≤ 7.5 mg/d prednisone equivalent at Baseline) must be tapered off within 4 weeks of the start of study drug.

All AbbVie personnel with direct oversight of the conduct and management of the trial (except for AbbVie Drug Supply Management Team) will be blinded to each subject's treatment through Week 12. The AbbVie study team will be unblinded to treatment assignment for the Primary Analysis. This unblinding will take place after all subjects have completed the Week 12 visit or have withdrawn from the study prior to Week 12. To maintain integrity of the trial, the study site personnel and the subjects will remain blinded until all subjects have either completed the last visit of LTE Period 1 or have withdrawn from the study. Blinded dosing regimens will be continued until the previous criteria are met. To maintain the blind, the ABBV-154 and placebo pre-filled syringes provided for the study will be identical in appearance. The IRT will provide access to unblinded subject treatment information in the case of a medical emergency.

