9.2.4 Summary of Long-Term Efficacy

Long-term efficacy in the LTE periods will be summarized using the As Observed case approach by treatment sequence (ABBV-154 40 mg EOW, ABBV-154 150 mg EOW, ABBV-154 340 mg EOW, ABBV-154 340 mg E4W, ABBV-154 150 mg EOW re-randomized from Placebo, ABBV-154 340 mg EOW re-randomized from Placebo).

- **As Observed (AO):** The AO analysis will be used for the summaries of long-term efficacy, which will not impute values for missing evaluations, and thus a

subject who does not have an evaluation on a scheduled visit will be excluded from the AO analysis for that visit.

- NRI-MI and MMRM will be used to summarize selected categorical and continuous efficacy variables, respectively, for long-term efficacy.

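### Protocol 5.8 keeps sites and subjects blinded throughout, but 4.1 and SAP 2.3 end the blind once all have finished LTE Period 1, and the by-visit LTE Period 2 efficacy summaries do not separate blinded from unblinded assessments

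*Protocol*

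**What the plan says.** The documents give two rules for how long sites and subjects stay blinded.

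- Protocol 5.8, the section on randomization and drug assignment: "The study site personnel and the subject will remain blinded throughout the study". No end point is given.
- Protocol 4.1: "study sites and subjects will remain blinded until all subjects have either completed the last visit of LTE Period 1 or have withdrawn". The Synopsis and Section 7.1 carry the same rule.
- SAP 2.3: "the study site personnel and the subjects will remain blinded until all subjects have either completed the last visit of LTE Period 1". It adds: "Blinded dosing regimens will be continued until the previous criteria are met".

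The rationale in Protocol Appendix F agrees with the second rule. It says that the second extension "will be blinded only until the last subject completes the last visit of Double-Blind Long-term Extension Period 1" or withdraws. This supports the reading of intent, but the conflict stands in current text without it.

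On analysis, SAP 9.2.4 says: "Long-term efficacy in the LTE periods will be summarized using the As Observed case approach by treatment sequence". It also applies NRI-MI and MMRM to selected long-term variables. SAP 9.5 analyses the primary and secondary variables at all assessed visits, including those in the extension periods. The extension-period MMRM in SAP 9.2.3 contains treatment, visit, their interaction, strata and baseline. None of these sections has a term, split or sensitivity analysis for blinding status.

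**The concern.** Section 5.8 is an operative statement on who is blinded and for how long. A site relying on it would expect the blind to last to the end of the study, and a site relying on 4.1 would not.

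The second rule also has an analytic consequence. Its trigger is the last subject's completion of LTE Period 1, whereas subjects roll into LTE Period 2 individually. At the trigger, early enrolees already have LTE Period 2 visits behind them and the last enrolee is only starting. The same study week can therefore hold assessments made with and without knowledge of the dose.

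ACR response, DAS28 (CRP) and CDAI depend on joint counts and on patient or physician global assessments. ACR response also uses pain and HAQ-DI. Only hsCRP is independent of the rater and the subject. Joint counts also feed the non-responder rule for stopping study drug in Protocol 5.4, so knowledge of dose could affect who remains on treatment.

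What is at stake is the description of long-term maintenance and of dose and regimen patterns. Section 4.2 of the protocol says the regimens were chosen to inform Phase 3 dose selection. A late drift or separation between sequences in LTE Period 2 could partly reflect the growing share of unblinded assessments.

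**Working it through.** **Inputs from the documents**

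- Period lengths: 12, 66 and 104 weeks (Protocol 4.1).
- Study drug is given by a professional "up to Week 78 (end of LTE Period 1"), which fixes the end of that period (Protocol 5.7).
- LTE Period 2 visits: Week 86 to Week 182 every 8 weeks, which is 13 visits (Protocol Appendix E).

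**Reproducing the plan's timeline**

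- 12 + 66 = Week 78; 78 × 7 + 1 = Day 547, as in Appendix E.
- 78 + 104 = Week 182; 182 × 7 + 1 = Day 1,275, as in Appendix E.

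**Assumptions (not in the documents)**

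- Uniform accrual over A weeks, with A from 13 to 104.
- Full retention, so that the last enrolee reaches Week 78.
- Unblinding takes place when the milestone is met. The documents give no date and do not say it is immediate.

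**Formula**

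The milestone falls A + 78 weeks after the first baseline. A subject enrolled at week e is then at study week A + 78 − e, which ranges from 78 (last enrolee) to 78 + A (first enrolee). The share still blinded at study week w is

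max(0, (A + 78 − w)/A) = max(0, 1 − (w − 78)/A).

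Example, A = 52 at Week 86: 1 − 8/52 = 85%. At Week 102: 1 − 24/52 = 54%. At Week 134: 1 − 56/52 is negative, so 0%.

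| Accrual A (weeks) | Study week at unblinding | Blinded, Week 86 | Blinded, Week 102 | Blinded, Week 134 | Mixed visits of 13 |
|---|---|---|---|---|---|
| 13 | 78–91 | 38% | 0% | 0% | 1 |
| 26 | 78–104 | 69% | 8% | 0% | 3 |
| 52 | 78–130 | 85% | 54% | 0% | 6 |
| 78 | 78–156 | 90% | 69% | 28% | 9 |
| 104 | 78–182 | 92% | 77% | 46% | 12 |

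Averaged over the 13 visits, the blinded share for A = 13 is (1 − 8/13)/13 = 3%. For A = 52 it is (6 − 8 × 21/52)/13 = 21%. For A = 104 it is (12 − 8 × 78/104)/13 = 46%.

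Two things follow. At every visit through Week 78 the share blinded is 100%, because the milestone cannot precede the last subject's own Week 78 under these assumptions. After Week 78 the blinded share falls until it reaches zero, so the unblinded share can only rise or stay flat. Under the 5.8 rule there would be no mixing at all.

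**The case against.** The strongest reply is that this is one sentence left unaligned. Four places agree on the rule, only LTE Period 1 is labelled double-blind, and SAP 2.3 ends blinded dosing at the same milestone. The intent is clear, and that lowers the risk. It does not remove a contrary instruction from the randomization section, nor does it supply the missing blinding status in the SAP.

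Second, the extension analyses are descriptive. Protocol 7.4 plans descriptive statistics by treatment sequence. The stated hypotheses are each dose against placebo at Week 12, everyone in LTE Period 2 is on ABBV-154, and no dose-versus-dose test is specified. This stands and limits the harm to how the tables are read.

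Third, randomization should balance enrolment time, so the blinded share at a given week should be similar across sequences apart from differential retention. Mixing alone does not confound the arms. What remains is knowledge-of-dose bias, as in any open-label extension, plus a time trend that moves with the unblinded share. This also stands.

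Fourth, the extent is assumed. With 13 weeks of accrual only one visit is mixed and most of LTE Period 2 is uniformly unblinded. The mixing figures do not measure bias.

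Stronger readings that the documents do not support:

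- A reader might infer that the adverse event tables mix blinding status at the same study week. SAP 10 summarises adverse events cumulatively by treatment group for Safety_PC and ALL_154. Its by-sequence summaries are of laboratory values and vital signs. ALL_154 does combine events from before and after unblinding, but not by week.
- A reader might infer that long-term efficacy rests on As Observed data alone. SAP 9.2.4 also uses NRI-MI and MMRM for selected variables, and NRI-MI generally counts early withdrawals as non-responders.

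**Conclusion.** The contradiction is real and lies in current text: the 5.8 rule and the 4.1/SAP 2.3 rule cannot both apply to a study with a 104-week LTE Period 2. Under the 4.1 rule, any spread in enrolment means subjects are unblinded at different study weeks, and SAP 9.2.4 and 9.5 do not distinguish the two states. Assuming uniform accrual over 13 to 104 weeks, full retention and unblinding at the milestone, 1 to 12 of 13 LTE Period 2 visits are mixed. The direction and size of any resulting bias cannot be derived from the documents.

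The reach is limited. It would be wrong to infer that the primary or secondary conclusions are at risk: Week 12 comparisons are untouched, and sites and subjects are blinded through Week 78 under either rule. The sponsor's study team is unblinded after the Primary Analysis, so that later protection is of sites and subjects only. The point concerns interpretation of LTE Period 2 and is worth correcting because the repair is cheap and depends on a date that must be recorded.

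**What to change.** 1. Protocol 5.8: align the sentence on site and subject blinding with Section 4.1 and SAP 2.3.
2. Record the date on which site and subject are unblinded, and derive a flag for each visit and event: before, or on or after, that date.
3. SAP 9.2.4/9.5: add a supportive summary of the LTE Period 2 subjective efficacy endpoints by that flag, within treatment sequence. Optionally, do the same in ALL_154 for investigator-assessed relatedness and for adverse events leading to discontinuation.
4. State in the SAP that long-term dose patterns will be interpreted mainly from the site- and subject-blinded data through Week 78, with LTE Period 2 as supportive.

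The cost is one protocol sentence, one recorded date, one derived variable and a few extra tables. Cells in the split tables will be smaller, and the blinded cells may be very small at later visits if accrual was short.
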